4. How many days did your productivity in household chores decrease by half or less in the last 3 months because of your headache? (Do not include the days you already counted in question 3 for not having done your chores).

5. How many days were you unable to participate in family, social and fun activities in the last 3 months because of your headache?

A. How many days did you have a headache in the last 3 months (if an attack lasted more than one day, count each day)?

B. On a scale of 0 to 10, how intense were those headaches on average (0: no pain, 10: worst pain imaginable)?

Score	Degree of Disability MIDAS
0-5 points	No or minimal disability
6-10 points	Mild disability
11-20 points	Moderate disability
>21 points	Severe disability

Stewart W F, et al. Validity of the Migraine Disability Assessment (MIDAS) score in comparison to a diary-based measure in a population sample of migraine sufferers. Pain 2000;88(1):41-52.

ANNEX 5

To whom it may concern:

We hereby inform you that the drug used in the clinical trial: "Efficacy of memantine compared to sodium valproate in the prophylactic treatment of migraine", a randomized controlled clinical trial, conducted by [name] [name], was donated by Laboratorios Torrent to support clinical research.

Under no circumstances did Torrent Pharma participate in the study, nor do we have access to any information about the patients, doses, or results.

SINCERELY

Laboratorios Torrent S. A. de C. V.

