1. To compare the efficacy in reducing the frequency of migraine attacks under prophylactic treatment with Memantine at a rate of 20 mg divided into two doses per day against sodium Valproate at a rate of 1000 mg divided into two doses per day for three months in adult patients with migraine.

B. Specific objectives

1. To evaluate the baseline frequency of migraine attacks in adult patients with migraine 28 days prior to the study.
2. To evaluate the frequency of migraine attacks of the group - treatment with sodium Valproate for three months, in adult patients with migraine.
3. To evaluate the frequency of migraine attacks of the group - treatment with Memantine for three months, in adult patients with migraine.

C. Secondary objectives

1. Evaluate the response rate to treatment.
2. Assess migraine disability using MIDAS (Migraine Disability Assessment) before and after treatment.
3. To assess pain intensity in migraine attacks with the visual analog scale (VAS) before and after treatment.
4. Identify adverse effects to sodium Valproate and Memantine.

SUBJECTS AND METHODS

Site

The study was conducted at the outpatient clinic of the Hospital Central [name] Prieto, San Luis Potosí.

Design

Prospective, randomized, double-blind, controlled clinical trial.

Inclusion criteria

1. Men and women from 18 to 65 years old.
2. Diagnosis of episodic migraine according to the ICHD-III of the IHS at least one year prior to the study.
3. Must present at ≥ 4 - ≤ 8 migraine attacks per month.
4. Not receiving prophylactic treatment for migraine headache.
5. Sign informed consent

Exclusion Criteria

1. Pregnant or breastfeeding patients.
2. Patients with other types of non-migraine headache.
3. Allergy to Sodium Valproate and/or Memantine
4. Being a carrier of systemic disease (infectious, immunological or metabolic processes) or cardiovascular disease (myocardial, coronary or valvular heart disease) that prevents participation in the study.

Elimination Criteria

1. Patients who do not tolerate the study drug during titration.
2. Patients who voluntarily leave the study.
3. Patients lost to follow-up.

Variables

Dependent's

1. Frequency of migraine attacks: Defined as the number of migraine attacks presented during the month. It is a continuous variable.
2. Treatment response rate: Defined as a decrease equal to or greater than 50% in the frequency of days with migraine compared to the baseline situation. It is a continuous variable.

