3. Migraine disability: Numerically defined according to the MIDAS (Migraine Disability Assessment) survey, (where 0-5=no disability, 6-10 points mild disability, 11-20 points moderate disability, and >21=severe disability). It is an ordinal variable.

4. Pain intensity: Numerically defined according to the visual analog scale (VAS) the pain intensity of the migraine attack before and after prophylactic treatment where 0=no pain and 10=very severe pain). It is a continuous variable.
5. Adverse treatment effects: Any response to a drug that is noxious, unintended and occurs at doses usual in our case for prophylactic treatment. The ICH Harmonised Tripartite guideline classifies any of the following: non-severe and severe, severe being any that results in death, is life threatening, requires hospitalization, results in disability.

Independent

1. Treatment

Group A: Memantine at a dose of 20 mg per day divided into two doses per day (morning and evening) for three months.

Group B: Sodium valproate at a dose of 1000 mg per day divided into two doses per day (morning and evening) for three months.

Confusers

1. Age: years completed by the patient. Migraine is most prevalent from 25 to 55 years of age, so it was expected that our patients would be young, and it was hoped that simple randomization would eliminate this bias.
2. Gender: is the organic condition that distinguishes men from women. It is a qualitative, nominal variable. The prevalence in women is higher with a 3:1 ratio between women and men, respectively. Therefore, a greater participation of women in the study was expected, 3 men in the Sodium Valproate group and 3 in the Memantine group participated and concluded the study.

Randomization method

By computer until the sample size is reached. Randomization will be performed by computer. Computer generated numbers will be used for the creation of a randomization sequence.

Method of follow-up.

Double blind, the blindness is for the investigator who does not know the assigned medication (blindness 1) and for the patient (blindness 2) who does not know the assigned medication. At the end of the visit, a third person, who is part of the research team, will give the medication (tablets for 4 weeks) and will be the only one who could open the blindness security code if necessary.

Work Plan

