Migraine with aura	3 (18.75%)	4 (23.52%)

Secondary objectives. - Treatment response rate which is referred to as the decrease of equal or more than 50% of migraine days. In the Memantine group with pretreatment migraine days 4.3 (SD+ 1.93) and post treatment 0.23 (SD+ 0.44) with a mean decrease in migraine days of 3.9 (SD+ 1.89) $p <<0.001$. In the Sodium Valproate group with pretreatment migraine days 5.5 (SD+ 1.25) and post treatment 0.27 with mean decrease of migraine days 4.88 with (SD+ 1.29) $p <<0.001$ ([Figure](#))

4). In both groups the 27 patients presented a successful treatment response rate, in the Memantine group with a decrease in percentage of migraine days average 94% (SD+ 9.95) and in the Sodium Valproate group 93.18% (SD+ 14.50).

The intensity of migraine was evaluated with the Visual Analog Scale (VAS) pre and post treatment. In the Memantine group pre-treatment VAS 8.5 (SD+ 1.36) and post-treatment 4.28 (3.65) $p < 0.00014$. In the VPA group with pretreatment VAS 8.94(SD+ 0.87) and post treatment 2.5 (SD+ 0.87) $p < 0.0000012$.

Migraine disability assessed with MIDAS in the Memantine group with MIDAS mean pretreatment 60.87 (SD+ 25.22) and post-treatment 15.57 (SD+ 14.32) $p < 0.000004$. In the Sodium Valproate group with MIDAS pretreatment of 51.92 (SD+ 22.67) and post treatment 10.53 (SD+ 19.97) $p < 0.00002$ ([Figure 5](#)).

Figure 5. MIDAS pre- and post-treatment in both groups.

Side effects: The side effects presented by the patients were not severe in their totality, eight patients in the Memantine group presented non-severe side effects and seven patients in the sodium valproate group ([Table 2](#)), the most frequent in both groups being somnolence.

Table 2 . Side effects

	Memantine	Sodium Valproate
None		
Drowsiness		
Lack of concentration		0
Parasomnia	0	1
Dizziness		0
Total		

DISCUSSION

This is the first randomized double-blind pilot clinical trial comparing the efficacy and safety of memantine with a first-line treatment, sodium valproate.

With the objective of recruiting 40 patients as a pilot study, the Neurology outpatient clinic was suspended due to the COVID-19 pandemic, we finally managed to recruit 33 patients, 3 lost follow-up and 3 dropped out of the study due to COVID-19 and only 27 patients were included.

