Being a carrier of systemic disease (infectious, immunological, or metabolic processes) or cardiovascular (myocardial, coronary, or valvular disease) prevents their participation in the study.

Primary outcomes

The primary outcome was the difference in change from baseline in the monthly attack frequency at week 12 between the two groups (using migraine diary).

Secondary outcomes

1. Evaluate the response rate to treatment.
2. Evaluate migraine disability using MIDAS (Migraine Disability Assessment) before and after treatment.
3. Identify adverse effects to sodium valproate and memantine.

Statistical analysis.

Statistical analysis

Descriptive statistical analysis of the variables of interest will be carried out.

For continuous variables, their research will be analyzed using the t-student test.

First, the number of participants (n) and the final analysis were calculated using R (56).

Alpha, the probability of a type 1 error was set to 0.05.

The power was set to 0.8, resulting in a type 2 error of 0.2.

Since we were limited to 20 participants per treatment, the delta was estimated with this restriction.

Since we were limited to 20 participants per treatment, the delta was estimated with this restriction.

Results

Table 1. Baseline Demographic and Clinical Characteristics

[figure not shown]
Characteristic	Memantine	Sodium Valproate	p
Female sex – no (%)	13(81.25%)	13 (76.47%)	
Male sex – no (%)	3 (18.75%)	4 (23.52%)	0.54*
Age	$31.18 \pm 10.94^{\$}$	$31.58 \pm 7.51^{\$}$	0.91*
A family history of migraine (%)	10 (62.5%)	9 (52.94%)	0.82*
Clinical characteristics			
Photophobia - no (%)	14 (87.50%)	16 (94.12%)	0.48*
Phonophobia - no (%)	16 (100%)	10 (58.82%)	0.60*
Nausea - no (%)	14 (87.5%)	17 (100%)	0.23*
Disability activities of daily living	15 (93.75%)	16 (94.12%)	0.74*
Migraine without aura	13 (81.25%)	13 (76.47%)	0.54*
Migraine with aura	3 (18.75%)	4 (23.52%)	

* Fisher's exact test

§ Plus-minus values are means \pm SD

PRIMARY OUTCOME

[figure not shown]
Monthly attack migraine frequency before and after treatment

Secondary outcome

Evaluate the response rate to the treatment

Figure 2. Days with migraine before and after treatment

Adverse Events

Table 2. Adverse Events According to Group

	Memantine (n=17)	Sodium Valproate (n=16)	Clinical severity CTCAE*
Any adverse event	8	7	
Somnolence	4	6	Grade 1-Mild
poor concentration	2	0	Grade 1-Mild
Parasomnia	0	1	Grade 1-Mild
Dizziness	2	0	Grade 1-Mild

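### MIDAS item 4, as printed in Annex 4, counts household days with a loss of at most half and omits larger partial losses, so that part of the score can rise as a patient improves

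*Protocol*

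**What the plan says.** Protocol Annex 4 (MIDAS), item 4, reads: "How many days did your productivity in household chores decrease by half or less in the last 3 months because of your headache". The bracketed note after it adds: "Do not include the days you already counted in question 3 for not having done your chores". Item 5 moves to another domain: "How many days were you unable to participate in family, social and fun activities in the last 3 months because of your headache". The two lettered questions that follow ask about headache days and average pain, and neither grades lost housework. Items 1 to 3 are not in the text available for this review, so question 3 is known only through item 4's reference to it.

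A higher score means more disability. Protocol, Variables, gives the bands: "where 0-5=no disability, 6-10 points mild disability, 11-20 points moderate disability, and >21=severe disability". MIDAS before and after treatment is a secondary objective in the Protocol and the second secondary outcome in the SAP ("Evaluate migraine disability using MIDAS (Migraine Disability Assessment) before and after treatment"). Protocol, Results, reports means of 60.87 before and 15.57 after treatment for memantine, and 51.92 and 10.53 for valproate. The Discussion reads the final means as moderate disability for memantine and mild for valproate.

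**The concern.** Items 3 and 4 work as a pair: item 3 takes the household days that were lost entirely, and item 4 should take the remaining days of substantial loss. The printed threshold points the wrong way. It admits days with a small loss and shuts out days with a large but incomplete one.

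Two things follow within the household domain. The second most disabling kind of day earns no point there. And the score is not monotone in disability, so a treatment that turns severe partial losses into mild ones pushes this part of the score up. If patients answered this wording literally, the household part of a secondary outcome would not measure what the printed bands are taken to grade, and the mild and moderate labels given to the two arms would rest partly on it.

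**Working it through.** The plan gives no figure to reproduce here; the check is of the item's logic. I assume that each counted day adds one point, because the scoring rule is not in the visible text.

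**1. Which threshold fits the item itself.** A day with no chores done is a 100% loss. It cannot also be a loss of at most half, so under the literal wording the instruction to leave out question 3 days would be redundant. The instruction is needed only if item 4 is meant to take days when productivity was reduced *to* half or less, that is, *by* half or more. The item's own text therefore points to the second reading.

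**2. Points per household day (items 3 and 4 together).**
- Literal rule: 1 if loss = 100% or 0% < loss ≤ 50%, otherwise 0.
- Reading that fits the exclusion: 1 if loss ≥ 50%, otherwise 0.

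| Loss of productivity | Literal | To half or less |
|---|---|---|
| 10% | 1 | 0 |
| 25% | 1 | 0 |
| 50% | 1 | 1 |
| 51% | 0 | 1 |
| 75% | 0 | 1 |
| 90% | 0 | 1 |
| 99% | 0 | 1 |
| 100% | 1 | 1 |

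The literal column goes from 1 to 0 and back to 1. Everything strictly between 50% and 100% scores nothing in this domain.

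**3. Reversal (day counts and loss levels are my assumptions).** Take 10 headache days that improve from 75% to 25% loss. The literal household score goes from 0 to 10; the other reading goes from 10 to 0. A mixed case: of 16 days, 4 have no chores done, 8 have a 70% loss and 4 a 30% loss, and treatment turns the eight 70% days into 30% days. Literal: 4 + 4 = 8 becomes 4 + 12 = 16. Other reading: 4 + 8 = 12 becomes 4 + 0 = 4.

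**4. Why no size or direction can be given.** Among partial-loss days, let *a* be those with a loss below half, *b* those at exactly half and *c* those above half. Literal item 4 = *a* + *b*; intended item 4 = *b* + *c*; error = (*a* + *b*) − (*b* + *c*) = *a* − *c*. The sign depends on the patient's mix of days. The error in a patient's change is (*a* − *c*) after treatment minus (*a* − *c*) before. The documents report no item-level data, so none of these terms is known.

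**5. What the error would be set against.**
- Falls in mean MIDAS: 60.87 − 15.57 = 45.30 (memantine) and 51.92 − 10.53 = 41.39 (valproate), a difference of 3.91.
- Difference in post-treatment means: 15.57 − 10.53 = 5.04.
- Labels: the valproate mean of 10.53 lies between the printed mild band (up to 10) and moderate band (from 11). It is 11 − 10.53 = 0.47 points short of moderate.

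An average error of a few days per patient would be as large as these gaps. Half a day would be enough to move the valproate label.

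**The case against.** The strongest reply is that this is a slip of translation. The site is in Mexico and the English text shows other signs of translation; the SAP's Conclusions, for example, abbreviate the pain scale as EVA where the Protocol uses VAS. One preposition, *by* for *to*, accounts for the anomaly, and patients may have completed a correctly worded form. This stands. A reader might infer that the reported MIDAS means are biased. The documents do not support that, because they do not show which wording patients saw or how they took it.

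A reader might also infer that large partial-loss days drop out of MIDAS altogether. That is shown only for the household domain. Such a day can still score under item 5 or under another domain's item, and items 1 to 3 could not be read. Nor can it be assumed that item 2 shares the wording.

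It is tempting to put a number on the error by taking a share of 60.87 as item 4. That does not work: 60.87 is the score obtained under whatever form was used, and the split of partial-loss days is unknown.

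Three further replies have partial force.
- Mean MIDAS fell steeply in both arms, with no sign of reversal. This is true of the totals, but fewer headache days can hide an opposite movement in one item.
- The outcome is secondary, and the primary outcome (diary attack frequency) is untouched. This stands and limits the weight of the point.
- Nothing suggests that the arms used different forms. That does not remove the problem, because *a* − *c* depends on each patient's mix of losses, which treatment changes.

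Finally, reported post-treatment migraine days are few: 0.23 and 0.27 per month, or 0.69 and 0.81 over three months if constant, which would leave little to misclassify. But even at five points per day, 0.69 days gives at most 3.45 points, against a reported mean of 15.57 (for valproate 4.05 against 10.53). Those day counts therefore cannot describe the whole MIDAS recall period and do not bound the error.

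**Conclusion.** Item 4 is wrong as printed. With its exclusion of question 3 days, it leaves household losses above half but short of total uncounted in items 3 and 4, and it makes the household part of the score non-monotone. This follows from the item's own text.

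The conclusion stops at the printed instrument. Bias in the reported MIDAS results is not shown, worsening of any patient's total is possible rather than certain, and no magnitude can be computed without item-level data. The point still deserves action: MIDAS is a stated secondary outcome, the post-treatment means differ by only 5.04 points, and the arms are given different disability labels. It rests on two assumptions: one point per counted day, and question 3 being what item 4 says it is.

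**What to change.** 1. Correct item 4 in Annex 4 so that it counts days when household productivity was reduced to half or less (that is, by half or more), keeping the exclusion of question 3 days. Check item 2 for the same wording.
2. Check the form that patients actually completed, in the language used, and state with the results which wording produced the reported scores.
3. Only if the administered form carried the printed wording: report MIDAS in both arms without the affected item or items and without the disability bands, and state this as a limitation.

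The cost is a form check and one wording correction. If the form was wrong, add one re-score and the loss of the band labels. The primary analysis does not change.

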"Efficacy of Memantine compared to sodium Valproate as prophylactic treatment for Episodic Migraine" A controlled randomized pilot clinical trial

A controlled randomized clinical trial

NCT04698525

ID 74-19

Study Protocol document date: February 15, 2019.

Statistical Analysis Plan document date: January 15, 2020.

Informed Consent Form document date: February 15, 2019.

STATISTICAL ANALYSIS PLAN

Sample size calculation

Normal distribution model: $x=Z(c/100)^2 r(100-r)$. $n=N x / ((N-1)E^2 + x)$ $E=\text{Sqrt}[(N-n)x / n(N-1)]$. With a margin of error of 5%, a confidence level of 95%, with a prevalence of migraine in the general population of the State of San Luis Potosi of 271800 with a distribution response of 15%.¹⁹ The recommended sample size is 196 participants. Because a pilot study will be conducted, 10% of the sample size will be taken to make it representative, a sample size of 20 participants for each group is decided.²⁰

Descriptive statistical analysis of the variables of interest will be performed. For continuous variables, analysis will be performed using the student's t-test. The number of participants (n) and the final analysis was calculated using R (56). Alpha, the probability of type 1 error was set to 0.05 and the power was set to 0.8 which resulted in the probability of a type 2 error of 0.2, given that we limited to 20 participants per treatment, delta was estimated with this restriction.

The aim of this study was to assess the efficacy of memantine and compared sodium valproate in the prophylactic treatment of migraine.

Study design

A single center, doble-blinded, controlled, randomized pilot clinical trial. The present study was designed as a randomized, double-blind, controlled pilot trial. It was authorized by the Research and Ethic Committee in February 2019, with the ID 74-19 and register in Clinical Trials from INH with the NCT04698525.

The study was conducted from July 2019 to November 2020 at Neurology service at Hospital Central [name] Prieto, San Luis Potosí, México.

Inclusion criteria

Men and women from 18 to 65 years old.

Diagnosis of migraine according to the ICHD-III of the IHS at least one year before the study.

To have at least 4-14 migraine attacks per month.

Not receiving prophylactic treatment for migraine

Sign informed consent

Exclusion criteria

Pregnant or lactating patients.

Patients with another type of non-migraine headache.

Allergy to Sodium Valproate and/or Memantine

Being a carrier of systemic disease (infectious, immunological, or metabolic processes) or cardiovascular (myocardial, coronary, or valvular disease) prevents their participation in the study.

Primary outcomes

The primary outcome was the difference in change from baseline in the monthly attack frequency at week 12 between the two groups (using migraine diary).

Secondary outcomes

1. Evaluate the response rate to treatment.
2. Evaluate migraine disability using MIDAS (Migraine Disability Assessment) before and after treatment.
3. Identify adverse effects to sodium valproate and memantine.

Statistical analysis.

Statistical analysis

Descriptive statistical analysis of the variables of interest will be carried out.

For continuous variables, their research will be analyzed using the t-student test.

First, the number of participants (n) and the final analysis were calculated using R (56).

Alpha, the probability of a type 1 error was set to 0.05.

The power was set to 0.8, resulting in a type 2 error of 0.2.

Since we were limited to 20 participants per treatment, the delta was estimated with this restriction.

Since we were limited to 20 participants per treatment, the delta was estimated with this restriction.

Results

Table 1. Baseline Demographic and Clinical Characteristics

[figure not shown]
Characteristic	Memantine	Sodium Valproate	p
Female sex – no (%)	13(81.25%)	13 (76.47%)	
Male sex – no (%)	3 (18.75%)	4 (23.52%)	0.54*
Age	$31.18 \pm 10.94^{\$}$	$31.58 \pm 7.51^{\$}$	0.91*
A family history of migraine (%)	10 (62.5%)	9 (52.94%)	0.82*
Clinical characteristics			
Photophobia - no (%)	14 (87.50%)	16 (94.12%)	0.48*
Phonophobia - no (%)	16 (100%)	10 (58.82%)	0.60*
Nausea - no (%)	14 (87.5%)	17 (100%)	0.23*
Disability activities of daily living	15 (93.75%)	16 (94.12%)	0.74*
Migraine without aura	13 (81.25%)	13 (76.47%)	0.54*
Migraine with aura	3 (18.75%)	4 (23.52%)	

* Fisher's exact test

§ Plus-minus values are means \pm SD

PRIMARY OUTCOME

[figure not shown]
Monthly attack migraine frequency before and after treatment

Secondary outcome

Evaluate the response rate to the treatment

Figure 2. Days with migraine before and after treatment

Adverse Events

Table 2. Adverse Events According to Group

	Memantine (n=17)	Sodium Valproate (n=16)	Clinical severity CTCAE*
Any adverse event	8	7	
Somnolence	4	6	Grade 1-Mild
poor concentration	2	0	Grade 1-Mild
Parasomnia	0	1	Grade 1-Mild
Dizziness	2	0	Grade 1-Mild

CTCAE v5.0 Common Terminology Criteria for Adverse Events

Conclusions

This double blind randomized clinical trial is the only pilot study where Memantine is compared to Sodium Valproate as prophylactic treatment for migraine.

The response of both groups was dramatic and significant ($p < 0.05$) to the management they received, with a clear difference in the number of attacks, duration of four, intensity (EVA), and disability caused by the attack (MIDAS)

Memantine could be considered as a prophylactic treatment option in migraine.

The adverse events were frequent but mild and transient for both groups.
